2. ANALYSIS SETS AND SUBGROUPS / TREATMENT GROUPS

2.1. Analysis sets

Intent-to-Treat (ITT) Analysis Set: The intent to treat (ITT) analysis set will consist of all subjects who have been randomized to the study. In accordance with the ITT principle, all subjects randomized will be kept in their originally assigned treatment group.

Modified Intent-to-Treat (mITT) Analysis Set: The mITT analysis set is a subset of the ITT analysis set. This set will consist of data from all subjects who have been randomized to the study and administered the IMP and had at least one treatment visit post IMP administration. This analysis set will serve as the primary analysis set for efficacy inference.

Per-Protocol (PP) Analysis Set: The per protocol (PP) analysis set is a subset of the mITT analysis set and will consist of all subjects with no major protocol violations that would be considered to impact the analysis of efficacy or safety.

Safety (ST) Analysis Set: The safety analysis set (ST) will consist of all subjects who have been randomized and received the Study IMP. This analysis set will be used as the primary set for safety inference.

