#### 7.3.2. Visit 5: 48-72 hours after IMP administration

If not hospitalized, the subject will return to the hospital 48-72 hours after the administration of the IMP. The following examinations will be performed on all patients:

- 1) Monitoring of blood pressure, heart rate, ECG and body temperature.
- 2) Physical examination, including local examination of the injected leg.
- 3) Pain scale assessment (VAS)

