#### 8.1.2. Exclusion Criteria

- A. Subject having on angiography (or other appropriate imaging modality) uncorrected aorto-iliac occlusive disease down to the origin of the profunda-femoris artery of the affected limb.
- B. Subjects who, in the opinion of the investigator, have a vascular disease prognosis that indicates they would require a major amputation (at or above the ankle) within approximately 4 weeks after administration of the IMP.
- C. Advanced CLI presenting as severe ischemic ulcers > 10 cm^2 or dry gangrene proximal to the metatarsophalangeal joint heads or lower extremity wet gangrene.
- D. Lower extremity non-treated active infection, e.g., wet gangrene, purulent discharge, cellulitis, MRSA infection.
- E. Body weight less than 45 kg (99 lbs).
- F. Hypercoagulable state, which is already known from the documented history.
- G. Subject received blood transfusion during the previous 4 weeks (to exclude the potential of non-autologous ACPs in the harvested blood).

- H. Subject's condition precludes - in 2 consecutive attempts - the manufacturing of batches that pass release specifications.
- I. Inability to communicate (that may interfere with the clinical evaluation of the subject).
- J. Major non-vascular operation during the preceding 3 months.
- K. Myocardial infarction or uncontrolled myocardial ischemia or persistent severe heart failure (New York Heart Association (NYHA) class IV) during the preceding 3 months.
- L. Severe aortic stenosis
- M. Renal failure where GFR is < 30 mL/min/1.73 m^2.
- N. Hepatic failure (Child-Pugh class C).
- O. Anemia (Hemoglobin lower than 11g/dl).
- P. Major stroke within the preceding 3 months resulting in debilitating hemiplegia.
- Q. Diagnosis of malignancy within the preceding 3 years (excluding non-melanoma skin cancers and non-metastatic prostate cancer).
- R. Concurrent chronic or acute infectious disease and uncontrolled infectious symptoms.
- S. Severe concurrent disease, e.g., septicemia, evident severe osteomyelitis, HIV-1,2/HBV/HCV/HTLV infections, poorly controlled insulin-dependent diabetes mellitus (HbA1c >10%), systemic lupus erythematosus, multiple sclerosis, amyotrophic lateral sclerosis, nephrotic syndrome, connective tissue disorders or arteritis (e.g., Takayasu arteritis).
- T. Bleeding diathesis.
- U. Participation at the same time in another investigational medicinal product or device study.
- V. Chronic immunomodulating or cytotoxic drug treatment.

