#### 14. CLINICAL STUDY PROCEDURE

Visit type	Screening		Adm. of IMP	Primary safety Follow-up		Long-term follow-up				
				4	5	6	7	8	9	10
Visit number	1	2	3	4	5	6	7	8	9	10
Consecutive visit day	-30 to -7	-7 ±1	0	1 (Phone f/u except for first 5 patients)	2-3	30 ±5	90 ±7	182 ±14	270 ±14	365 ±14
Demography	X									
History	X									
Physical exam	X		X	X (only first 5 subjects)	X	X	X	X	X	X
Rutherford Assessment	X		X			X	X	X	X	X
Leg assessment, bilaterally (skin, swelling, temperature, ulcers, gangrene, etc.)	X		X	X (only first 5 subjects)	X	X	X	X	X	X
Heart rate, BP, ECG & Temperature	X		X (before admin of IMP and 2 hours after)	X (only first 5 subjects)	X	X	X	X	X	X
Eligibility assessment	X									
Consent form signing	X									
Pain scale assessment (VAS)	X			X	X	X	X	X	X	X
Analgesia drugs and doses	X					X	X	X	X	X

Visit type	Screening		Adm. of IMP	Primary safety Follow-up		Long-term follow-up				
				4	5	6	7	8	9	10
Visit number	1	2	3	4	5	6	7	8	9	10
Laboratory tests	X	X			X (only first 5 subjects)	X	X	X	X	X
Screening for HIV,HTLV, HBV,HVC	X									
Pregnancy test	X									
Ankle pressure, bilaterally	X					X	X	X	X	X
Toe pressure, bilaterally	X					X	X	X	X	X
Vascular Quality of Life Questionnaire	X					X	X	X	X	X
Ulcer assessment, size and photography, bilaterally.	X		X			X	X	X	X	X
Telephone follow-up				X (at night)						
Blood cultures		X			X (only first 5 subjects)					
Blood draw for manufacture of investigational medicinal product		X								
IMP administration			X							

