## **20.7. Efficacy Assessment**

The following trial end-points will be calculated and statistically analyzed for the ITT cohort which will serve as the primary analysis set for efficacy inference.

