3.3. Efficacy analysis

Efficacy analyses will be carried out in the mITT analysis set by treatment arm.

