3.3.2. Primary efficacy endpoint

3.3.2.1. Definition

The primary efficacy endpoint for this study is the earlier time from treatment with IMP to either de-novo gangrene in the treated limb, or doubling of wound size in the treated limb, or major amputation in the treated limb, or death. For subjects who were lost to follow-up or completed Month 12 study visit without a study event, the time to event will be censored by the subject's last follow-up date in the study.

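### The primary mITT set requires a visit after injection, so an injected subject who dies before any visit has a primary event but is left out of the primary analysis

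*SAP*

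**What the plan says.** SAP 2.1 defines mITT as randomised subjects who were "administered the IMP and had at least one treatment visit post IMP administration" and names it the primary set for efficacy inference. SAP 3.3 repeats this: "Efficacy analyses will be carried out in the mITT analysis set by treatment arm".

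The endpoint in SAP 3.3.2.1 is "the earlier time from treatment with IMP to either de-novo gangrene in the treated limb", with doubling of wound size in that limb, "or major amputation in the treated limb, or death". The clock starts at injection.

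Protocol 20.5 has the same mITT wording but does not make that set primary. Protocol 20.7 says the endpoints will be "statistically analyzed for the ITT cohort which will serve as the primary analysis set for efficacy inference".

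The Safety set, in both documents, is everyone randomised and injected, with no visit condition.

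On timing, the Protocol Section 14 table puts Visit 4 on Day 1, by telephone for all but the first five subjects. Under Protocol 7.3.2, if not already in hospital, "the subject will return to the hospital 48-72 hours after the administration of the IMP" for Visit 5.

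**The concern.** Beyond injection itself, membership of the primary set depends on something that happens after treatment: being seen again. Death is a primary event, and it prevents any later visit. The rule therefore selects the primary set partly on the outcome being compared.

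The condition also does no useful work in a time-to-event analysis. An injected, event-free subject who never returns would be censored at or near Day 0 and contribute essentially nothing. The visit condition can materially change the primary result only by removing events. The events at risk are the earliest deaths after an injection procedure, and those subjects stay in the Safety set while leaving the efficacy comparison.

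**Working it through.** **Is an excluded subject recovered anywhere?** Take a subject injected on Day 0 who dies on Day 1 with no visit in between.

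- SAP 3.3.2.1: primary event at Day 1.
- SAP 2.1: not in mITT, and so not in per-protocol, which is a subset of mITT.
- SAP 3.3.2.3: the planned sensitivity analyses are an unstratified test and Cox model, the per-protocol set, and three analyses of censoring. Under SAP 3.3 they work within mITT. Counting discontinued subjects as events cannot reach someone who is not in the set.
- No ITT or all-injected efficacy analysis is planned.

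**Planned power (SAP 1.3).** Inputs: 51 events, hazard ratio 0.43, one-sided 2.5%, 2:1 allocation. Schoenfeld's formula gives power = Φ(√(d × 1/3 × 2/3) × |ln HR| − 1.96).

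- d = 51: √11.33 = 3.367; 3.367 × 0.844 = 2.841; Φ(0.881) = 81.1%. The stated 81% is reproduced.
- d = 50, 49, 48: 80.3%, 79.5%, 78.7%, or about 0.8 points per lost event.

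**Events before the first in-person visit.** Inputs: medians of 3 months (placebo) and 7 months (ACP-01), exponential; 65 subjects split 2:1 (21.7 and 43.3); 30.44 days per month; Day 3 as the latest scheduled time of Visit 5.

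- Placebo: 1 − exp(−(ln 2/3) × 3/30.44) = 2.25%; × 21.7 = 0.49.
- ACP-01: 1 − exp(−(ln 2/7) × 3/30.44) = 0.97%; × 43.3 = 0.42.
- Total by Day 3: 0.91. The same sum to Day 1 gives 0.30.

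SAP 1.3 reports a pooled interim median of 241 days, longer than even the 7-month planning median (7 × 30.44 = 213 days). Treating it as exponential: 65 × (1 − exp(−ln 2 × 3/241)) = 0.56 by Day 3.

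These counts include all four event types. Only deaths before any visit, and amputations with no visit ever after, would be lost. As an illustration, if deaths were 10% to 30% of events (my assumption; the documents give no such split), 0.91 becomes about 0.1 to 0.3 subjects.

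**Effect of one lost event on the hazard ratio.** This is a rough rate-ratio calculation; the person-time lost with the subject is negligible. Over 12 months the planning medians give 30.1 events on ACP-01 and 20.3 on placebo. Scaled to 51 these become 30.46 and 20.54.

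- One ACP-01 event removed: 29.46/30.46 = 0.967, about 3% lower.
- One placebo event removed: 20.54/19.54 = 1.051, about 5% higher.

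**The case against.** The case that this is only a wording point has real substance.

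- **Limb loss.** A reader might infer that every early amputee is dropped. The rule asks for one visit at any time after injection, not before the event. A subject amputated on Day 1 and seen later, including at Visit 5 while still in hospital, stays in mITT with the event. Exclusion B also removes subjects whose prognosis indicates that "they would require a major amputation (at or above the ankle) within approximately 4 weeks after administration of the IMP".
- **The term.** A reader might call the condition unworkable because Visit 3 is the only visit headed as treatment. But Protocol 20.8.2 to 20.8.3 and SAP 3.5.2 to 3.5.4 use the phrase for scheduled visits after baseline. It is loose but usable. Whether the Day 1 telephone contact counts is not stated.
- **The window.** Reading the rule as requiring the Month 1 visit would expose about 8.4 composite events by Day 30. Nothing supports that reading, since Visits 4 and 5 come first. The exposed window is two to three days, and possibly only hours, because Protocol 7.3.1 describes the two-hour observation under Visit 4 (the Section 14 table lists it under Visit 3).
- **Direction.** A reader might infer a bias in favour of ACP-01. Deletion can only lower the event count, but the hazard ratio moves either way by arm. The planning hazards put slightly more of the lost events on placebo (0.49 against 0.42).
- **Visibility.** SAP 3.2.1 tabulates treated subjects, analysis-set membership and deaths among discontinuation reasons by arm, and deaths are listed for the Safety set. An exclusion would be seen, although the primary estimate would still omit it.

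What remains is the death before any visit and the amputee never seen again. Each has a primary event, is outside mITT, and is not restored by any planned analysis.

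**Conclusion.** The rule is a defect in how the primary set is defined, with a small expected effect. At most about 0.6 to 0.9 subjects would be lost under the plan's own figures, and probably far fewer. That range assumes a constant hazard from Day 0, a first visit by Day 3 and 65 subjects. The eligibility exclusions and injection-day fitness check would push the early hazard down; an excess of deaths tied to the procedure, which the planning model does not contain, would push it up.

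There is little slack to absorb a loss. The planning medians give about 50.4 events in 65 subjects over a full 12 months (30.1 + 20.3), against the 51 required.

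The documents do not show that anyone has been excluded this way. The shortest follow-up of 1 day at the interim export does not show it. SAP 1.3 counts 65 subjects treated and followed at the interim and 65 evaluable for the final analysis, which is consistent with no exclusion but does not prove it.

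The correction is still worth making, because primary-set membership should not depend on surviving to a visit.

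**What to change.** In SAP 2.1, delete the second condition in "administered the IMP and had at least one treatment visit post IMP administration", the one about a later visit. The primary mITT set then becomes all randomised and injected subjects, analysed as randomised, which is the membership the Safety set already has. State that a subject with no later data and no known event is censored at injection. Report any injected subject otherwise left out of an efficacy analysis, by arm and event status.

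Align the mITT wording in Protocol 20.5 at the next amendment. In the same step, reconcile the SAP's choice of mITT as primary with the protocol's choice of ITT. If ITT is kept, a time origin is needed for subjects randomised but never injected, because the clock starts at injection.

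The SAP change is one clause and needs no new data. The restored subjects also enter the two secondary analyses, where SAP 3.3.3 already assigns a worst-case value to early terminators and to those with an event. The protocol edit needs ethics approval before implementation (Protocol Section 11).

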#### **20.5. Analysis Sets**

- Intent-to-Treat (ITT) Analysis Set: The intent to treat (ITT) analysis set will consist of all subjects who have been randomized to the study. In accordance with the ITT principle, all subjects randomized will be kept in their originally assigned treatment group. This analysis set will serve as the primary analysis set for efficacy inference.
- Modified Intent-to-Treat (mITT) Analysis Set: The mITT analysis set is a subset of the ITT analysis set. This set will consist of data from all subjects who have been randomized to the study and administered the IMP and had at least one treatment visit post IMP administration.
- Per-Protocol (PP) Analysis Set: The per protocol (PP) analysis set is a subset of the mITT analysis set and will consist of all subjects with no major protocol violations as will be defined in a more detailed Statistical Analysis Plan (SAP) to be written prior to revealing of the blind and having follow up assessments available.

- Safety (ST) Analysis Set: The safety analysis set (ST) will consist of all subjects who have been randomized and received the Study IMP. This analysis set will be used as the primary set for safety inference.

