## **20.6. Demographics and Baseline Characteristics**

Demographics and baseline data will be described for the ITT analysis set. Subject demographics and baseline characteristics, including underlying disease history, medical history and prior medications will be compared between the study groups to assess baseline comparability. Continuous variables (e.g., subject age, weight, height, and body mass index (BMI)) will be summarized using descriptive statistics (number [n], mean, standard deviation, and standard error, median, minimum, and maximum) Categorical variables will be summarized using subject counts and percentages. Categories for missing data will be presented if necessary.

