### **20.8.4. Statistical Analysis Plan (SAP)**

A more detailed SAP will be developed while the study is still ongoing, prior to revealing of the study blind and the conduct of the futility analysis and will be submitted for the review of the Division. This

SAP will also outline the sensitivity analyses to be performed for the primary study endpoint using other set of methods accounting for the missingness mechanism as well as assessment of other analysis sets allowing to evaluate the robustness and internal consistency of primary results and conclusions.

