1. INTRODUCTION

This Statistical Analysis Plan (SAP) details the planned analyses to be performed, in accordance with the main characteristics of the study protocol. The protocol version in effect at the time of this analysis was 5.5.

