3.2.2. Demographic and baseline characteristics

Demographics and baseline data will be described for the mITT analysis set. Subject demographics and baseline characteristics, including underlying disease history, medical history and prior medications will be compared between the study groups to assess baseline comparability. Continuous variables (e.g., subject age, weight, height, and body mass index (BMI)) will be summarized using descriptive statistics (number [n], mean, standard deviation, and standard error, median, minimum, and maximum). Categorical variables will be summarized using subject counts and percentages. Categories for missing data will be presented if necessary.

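### The SAP moves the primary efficacy set and the baseline set from ITT to mITT, against protocol 5.5, gives no reason, and plans no efficacy analysis on ITT

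*SAP*

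**What the plan says.** Protocol 20.5 defines ITT as everyone randomised and adds: "all subjects randomized will be kept in their originally assigned treatment group. This analysis set will serve as the primary analysis set for efficacy inference". Protocol 20.7 repeats this for all the efficacy endpoints that follow, which are to be "analyzed for the ITT cohort which will serve as the primary analysis set for efficacy inference". For the baseline table, Protocol 20.6 says: "Demographics and baseline data will be described for the ITT analysis set". The protocol also defines mITT but gives it no primary role.

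The SAP introduction describes the planned analyses as "in accordance with the main characteristics of the study protocol. The protocol version in effect at the time of this analysis was 5.5". SAP 2.1 keeps both definitions, but the primary-set sentence now follows mITT, whose members must be randomised, dosed, and have "had at least one treatment visit post IMP administration. This analysis set will serve as the primary analysis set for efficacy inference". SAP 3.3 states: "Efficacy analyses will be carried out in the mITT analysis set by treatment arm". SAP 3.2.2 states: "Demographics and baseline data will be described for the mITT analysis set". No passage mentions or explains a departure.

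**The concern.** A reader of the protocol expects the single primary test to compare the arms as randomised. A reader of the SAP will see it run on dosed subjects with a later visit. Both exclusions act after randomisation, so the comparison is protected only if they fall equally on the arms or are very few. The protocol foresees subjects who are never dosed. A second failed batch leads to withdrawal (7.2), and a subject found unfit on the injection day is discontinued uninjected and may be re-screened (7.2.1).

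If the documents stay as they are, the trial reports its primary result on a set its protocol did not name, with no stated reason. It would also have no planned efficacy result on the named set to compare it with.

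**Working it through.** **1. The texts side by side**

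| Role | Protocol 5.5 | SAP |
|---|---|---|
| Primary efficacy set | ITT (20.5, 20.7) | mITT (2.1, 3.3) |
| Baseline table | ITT (20.6) | mITT (3.2.2) |
| Safety set | Randomised and dosed (20.5) | Same (2.1) |

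**2. Did the protocol leave this choice to the SAP?** Protocol 20.5 leaves it the major violations that define per-protocol. Protocol 20.7.1 leaves it the prognostic factors and the sensitivity analyses. Protocol 20.8.4 leaves it "assessment of other analysis sets allowing to evaluate the robustness and internal consistency of primary results and conclusions". Testing the robustness of a primary result on other sets presupposes that the primary set is fixed. None of these passages lets the SAP replace it.

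**3. Does any SAP efficacy analysis use ITT?** SAP 3.3.2.3 lists an unstratified test and Cox model, a per-protocol analysis, and three analyses of informative censoring. The subgroup analyses (3.3.4) fall under the mITT rule of 3.3. The exploratory section (3.4) names no set. ITT appears only as a definition (2.1) and in the disposition counts (3.2.1).

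**4. How far apart are the sets?** The documents do not say. The one count, 65 subjects enrolled, treated and followed at the April 2020 data export (SAP 1.3), shows no gap. Batch failure may add little: blood is drawn from every subject, the batch rule is not arm-specific, two failures is exclusion criterion H, and randomisation follows eligibility (Protocol 7.1.2, 7.2, 8.1.2, 20.1). Injection-day discontinuation and missed post-IMP visits remain possible, in unknown number.

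**5. The plan's own figure.** SAP 1.3 gives 51 events, hazard ratio 0.43, one-sided 2.5%, 81% power. By Schoenfeld with 2:1 allocation, z = √(51 × 2/3 × 1/3) × |ln 0.43| − 1.96 = 3.367 × 0.844 − 1.96 = 0.881, so power is 81.1%. It reproduces. At 12 months, 65 subjects split 43:22 give 43 × (1 − 2^(−12/7)) + 22 × (1 − 2^(−12/3)) = 29.9 + 20.6 = 50.5 expected events. The choice of set changes neither figure.

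**6. Illustration of size.** From the plan: exponential medians of 7 and 3 months, 12 months of follow-up after IMP, 65 treated as 43:22. Assumed: the number untreated; placebo hazard for them; withdrawal at 0.25 to 1 month; a lag from randomisation to IMP of 7 days in 90% and 28 days in 10%. The lag borrows Visit 2 at day −7 and the 21-day repeat window, because no passage dates randomisation. The test is an unstratified log-rank at one-sided 2.5%, with the median Cox estimate over 20,000 runs. With nobody untreated, the hazard ratio is 0.42 and power 84.5%.

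| Untreated (ACP-01, placebo) | ITT, censored: HR (power) | ITT, placebo rate imputed: HR | ITT, counted as events: HR |
|---|---|---|---|
| 2, 1 | 0.43 (84.8%) | 0.44 | 0.45 |
| 4, 2 | 0.43 (83.8%) | 0.46 | 0.46 |
| 6, 3 | 0.43 (83.7%) | 0.47 | 0.49 |
| 2, 0 | 0.43 (84.4%) | 0.44 | 0.46 |
| 4, 0 | 0.43 (83.1%) | 0.46 | 0.50 |
| 6, 0 | 0.44 (82.7%) | 0.48 | 0.54 |

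A repeat with 6,000 runs per case agreed within 0.01 on the hazard ratio. Fixing the lag at 0, 7 or 28 days in the (6, 3) and (6, 0) cases kept the censored hazard ratio at 0.43 to 0.44.

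**7. Type I error.** With no drug effect, a common median of 5.2 or 7.9 months, and 3 to 20% of both arms (frailer subjects, hazard ×1.5 or ×3) left untreated, one-sided error was 2.9 to 3.3% on mITT and on censored ITT, against 3.0 to 3.2% with nobody removed (40,000 runs). The excess over 2.5% belongs to the log-rank test at this size and allocation, and partly explains why simulated power exceeds 81%.

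**The case against.** The strongest reply is that the protocol's ITT rule cannot be applied as written. The endpoint clock runs from IMP in both documents, and the sample size counts treated subjects, so an undosed subject has no time zero. SAP 3.3.2.1 ties limb events to the treated limb, which such a subject lacks, and wound doubling needs a reference measurement. This stands as a possible reason for mITT, and it means that restoring ITT brings a departure of its own. But the SAP does not offer it as the reason, and the protocol names both the IMP clock and ITT.

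It is also fair that an ITT analysis with early censoring says little about the subjects left out. That stands too: only runs that assume or impute their outcomes move, and they move by assumption.

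A reader might infer more than the documents support:

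- **That the primary analysis is undefined.** The SAP is explicit and consistent in itself. The defect is an undeclared departure from the protocol.
- **That the set was changed because of results.** SAP 1.3 reports an interim comparison of the arms, so the text postdates that look. But Protocol 20.2 gives interim analyses to an independent party that keeps the sponsor blinded, and no passage links the change to results.
- **That loss differed by arm.** Protocol 7.2.1 gives the injection-day check to an investigator it calls unblinded, whereas Section 7 says only that the injector may become unblinded while injecting. Equal loss is therefore not guaranteed, but nothing shows unequal loss.
- **That the effect is large.** A hazard ratio of 0.54 needs six untreated subjects, all in ACP-01 and all counted as events. No passage supports that.

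**Conclusion.** The mismatch is certain. The SAP replaces the protocol's primary efficacy and baseline set, gives no reason, goes beyond what the protocol delegated, and plans no efficacy analysis on ITT. It should be corrected before unblinding.

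Its numerical effect cannot be determined from the documents and may be small. If few subjects went undosed, or batch failures preceded randomisation, the sets nearly coincide. With untreated subjects censored, ITT gives 0.43 to 0.44 in every case tried. With loss equal by arm, mITT showed no excess type I error over ITT.

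The simulated power is for an unstratified test, whereas SAP 3.3.2.2 stratifies. It uses the planned medians, although SAP 1.3 reports a pooled median of 241 days, and it assumes the lag and the untreated counts. It shows direction and rough size and is not a forecast.

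**What to change.** Before unblinding:

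1. **Reconcile the documents.** Either restore ITT as the primary and baseline set in SAP 2.1, 3.2.2 and 3.3, or keep mITT with a dated reason and a matching protocol amendment. In the second case, add an ITT analysis of the primary endpoint to 3.3.2.3.
2. **Write the ITT rules for untreated subjects.**
   - Measure time from randomisation, declared as a departure from the IMP-based clock in Protocol 10.1.1 and 20.7.1 and SAP 3.3.2.1.
   - Use the limb selected at screening (Protocol 7.1) for limb events.
   - Take the last ulcer measurement before randomisation, otherwise Visit 1, as the reference for wound doubling.
   - Count a re-screened person once, under the first assignment.
   - Censor at last contact in the main ITT analysis. Include these subjects in the runs of 3.3.2.3 that count discontinuation as an event or use the placebo-based model, because the censored analysis alone cannot show the effect of leaving them out.
3. **Report the exclusions.** In 3.2.1, tabulate by arm and reason the randomised but untreated subjects, and the dosed subjects dropped for lack of a post-IMP visit.
4. **State the set for the secondary endpoints**, and declare it if it differs from Protocol 20.7.

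The cost is wording in SAP 2.1, 3.2.1, 3.2.2, 3.3 and 3.3.2.3, a statement on time zero or a protocol amendment, and the primary model plus two already planned sensitivity methods run on ITT. The price in precision is small under censoring. The stress runs will show some dilution if there are untreated ACP-01 subjects. If the secondary endpoints stay on treated subjects, they will sit on a different set from an ITT primary analysis.
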